15.2 Potential Risks

Alterations in Wound Healing or Repair of Tissue Damage

Due to the involvement of TGF β in tissue and skin repair, alterations in wound healing or repair of tissue damage is considered an important potential risk. No relevant event is reported in the ongoing M7824 clinical studies. Monitoring of any surgical wounds while on study is recommended. In general, a 2-week delay from treatment is recommended following minor surgery and 4 week delay for major surgery.

Embryo-fetal Toxicities

Embryo-fetal toxicities are a known risk of the PD-1/PD-L1 targeting class. Animal models link the PD-1/PD-L1 signaling pathway with maintenance of pregnancy through induction of maternal immune tolerance to fetal tissue (Guleria, 2005; Leber, 2010; Wafula, 2009; Zenclussen, 2013). Embryo-fetal and reproductive toxicities have also been investigated in animal models for a humanized monoclonal antibody targeting TGF β 1. At doses as high as 30 mg/kg, no maternal reproductive toxicity or embryo-fetal lethality were observed in rabbits (Hilbush, 2016). To mitigate these potential risks, pregnant participants are excluded from the study, and all participants of childbearing/conceiving potential must use highly-effective contraception.

Mild to Moderate Mucosal Bleeding Events

Mucosal bleeding events of mild to moderate severity were observed in participants treated with M7824 in ongoing studies and are a potential risk for M7824. Events may include epistaxis, hemoptysis, gingival bleeding, or hematuria among others. In general, majority of these events were observed to be self-limiting, did not require intervention, and resolved without discontinuation of study treatment.

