10.0 Ocular Toxicities

All recommendations are expert consensus based, with benefits outweighing harms, and strength of recommendations are moderate.

Abbreviations: ICPi, immune checkpoint inhibitor; G, Grade; irAE, immune-related adverse event; IV, intravenous, TNF, tumor necrosis factor.

**Appendix 2 Adverse Events: Definitions and Procedures for Recording, Evaluating, Follow-up, and Reporting
Definitions Adverse**

Event

An adverse event is the appearance or worsening of any undesirable sign, symptom, or medical condition occurring after the first protocol intervention, even if the event is not considered to be related to study treatment. Medical conditions/diseases present before starting study therapy are only considered adverse events if they worsen after starting study treatment. Abnormal laboratory values or test results constitute adverse events only if they induce clinical signs or symptoms, are considered clinically significant, or require therapy.

For surgical or diagnostic procedures, the condition/illness leading to such a procedure is considered as the AE rather than the procedure itself.

Compared to baseline (Screening or the Week 1, Day 1 visit), medical conditions that do not worsen in severity or frequency during the study are defined as baseline medical conditions, and are NOT to be considered as AEs.

All newly diagnosed or worsening pre-existing conditions (clinically significant changes in frequency, and/or intensity), signs, and symptoms observed from baseline (Screening or the Week 1, Day 1 visit), whether related to study intervention or not, are to be reported as AEs.

Progression of the cancer under study is not considered an AE.

The Investigator is required to grade the severity or toxicity of each AE.

Investigators will reference the National Cancer Institute - Common Terminology Criteria for AEs (CTCAE), version 5.0 (publication date: 27 Nov 2017), a descriptive terminology that can be used for AE toxicity grade reporting.

A general grading (severity/intensity; hereafter referred to as severity) scale is provided at the beginning of the above referenced document, and specific event grades are also provided.

If the severity for an AE is not specifically graded by NCI-CTCAE, the Investigator is to use the general NCI-CTCAE definitions of Grade 1 through Grade 5, using his or her best medical judgment.

The 5 general grades are:

Grade 1 or Mild

Grade 2 or Moderate Grade 3

or Severe

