Medical conditions present at the initial study visit that do not worsen in severity or frequency during the study are defined as baseline medical conditions, and are not to be considered AEs.

AE/SAEs Observed in Association with Disease Progression

Progression of the disease/disorder being studied assessed by measurement of lesions on radiographs or other methods as well as associated clinical signs or symptoms (including laboratory abnormalities) should not be reported as an (S)AE, unless the patient's general condition is more severe than expected for the participant's condition and/or unless the outcome is fatal within the adverse event reporting period.

Adverse Events of Special Interest

Adverse events of special interest can be serious or nonserious events; however, must always be reported on the SAE/AESI Report Form, and will follow the procedure described below for reporting SAEs and AESIs.

Categories of AESIs related to M7824 include:

- Infusion-related reactions including immediate hypersensitivity
- Immune-related adverse events
- Potential TGF β -mediated skin adverse events
- Treatment-related anemia adverse events

Recording and Follow-Up of AE and/or SAE

It is important that each AE report include a description of the event, its duration (onset and resolution dates and also onset and resolution times, when it is important to assess the time of AE onset relative to the recorded study intervention administration time), its severity, its causal relationship with the study intervention, any other potential causal factors, any treatment given or other action taken, including dose modification or discontinuation of the study intervention, and its outcome. In addition, serious cases should be identified and the appropriate seriousness criteria documented.

Reporting Serious Adverse Events and Adverse Events of Special Interest Serious Adverse Events

All events occurring during the conduct of a protocol and meeting the definition of a SAE must be reported to the IRB in accordance with the timeframes and procedures outlined in "The University of Texas M. D. Anderson Cancer Center Institutional Review Board Policy for Investigators on Reporting Serious Unanticipated Adverse Events for Drugs and Devices". Unless stated otherwise in the protocol, all SAEs, expected or unexpected, must be reported to the IND Office, regardless of attribution (within 5 working days of knowledge of the event).

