In the event of a nonserious AESI, the Investigator will notify EMD Serono by completing the AESI Report Form within 24 hours. Serious AESIs must be reported in an expedited manner as SAEs as outlined above.

Reporting of nonserious AESIs via paper report form is required as a back-up method only in the case of EDC failure. Names, addresses, and telephone and fax numbers will be included on the paper report form.

The investigator (or physician designee) is responsible for verifying and providing source documentation for all adverse events and assigning the attribution for all adverse events for subjects enrolled.

Recommended Adverse Event Recording Guidelines

Attribution	Grade 1	Grade 2	Grade 3	Grade 4	Grade 5	
Unrelated	Phase I	Phase I	Phase I Phase II	Phase I Phase II Phase III	I II III	Phase I Phase II Phase III
Unlikely	Phase I	Phase I	Phase I Phase II	Phase I Phase II Phase III	I II III	Phase I Phase II Phase III
Possible	Phase I Phase II Phase III	I II III	Phase I Phase II Phase III			
Probable	Phase I Phase II Phase III	I II III	Phase I Phase II Phase III			
Definitive	Phase I Phase II Phase III	I II III	Phase I Phase II Phase III			

Serious Adverse Event (SAE) Reporting

An adverse event or suspected adverse reaction is considered “serious” if, in the view of either the investigator or the sponsor, it results in any of the following outcomes:

- Death
- A life-threatening adverse drug experience – any adverse experience that places the patient, in the view of the initial reporter, at immediate risk of death from the adverse experience as it occurred. It does not include an adverse experience that, had it occurred in a more severe form, might have caused death.
- Inpatient hospitalization or prolongation of existing hospitalization
- A persistent or significant incapacity or substantial disruption of the ability to conduct normal life functions.
- A congenital anomaly/birth defect.

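### Appendix 2 requires every adverse event to be reported whatever its cause, but its recording table leaves out Grade 1-2 unrelated and unlikely events for Phase II; the two must be reconciled

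*Combined protocol and SAP*

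**What the plan says.** Appendix 2 opens by defining an adverse event as any new or worsening undesirable sign, symptom or condition after the first protocol intervention, "even if the event is not considered to be related to study treatment". A few paragraphs later it repeats the rule for newly diagnosed or worsening conditions: these, "whether related to study intervention or not, are to be reported as AEs". Neither statement has a grade threshold. The same text equates Grade 1 with mild and Grade 2 with moderate. Its causality paragraphs define two levels, Unrelated and Related.

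Towards the end of the same appendix stands a table headed "Recommended Adverse Event Recording Guidelines". It crosses five attribution levels (Unrelated, Unlikely, Possible, Probable, Definitive) with Grades 1 to 5 and shows in each cell the trial phases for which the event is recorded.

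Sections 5.1 and 15.2 name mild-to-moderate mucosal bleeding as a potential risk of M7824: "Events may include epistaxis, hemoptysis, gingival bleeding, or hematuria among others". The list of adverse events of special interest (AESIs) in Appendix 2 has four categories: infusion reactions, immune-related events, TGFβ-mediated skin events, and "Treatment-related anemia adverse events". Bleeding is not among them. Section 6.2 makes toxicity, graded by CTCAE version 5, a secondary endpoint.

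**The concern.** The definition and the table lead to different databases. Under the definition, a Grade 1 or 2 event enters whatever its cause. Under the table, it enters a Phase II trial only if the investigator judges it at least possibly related. The trial is open-label and single-arm, so that judgement is unblinded and there is no control group to show how many such events would be expected without the drug.

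What is at stake is the meaning of any all-cause toxicity rate. Two sites or data coordinators could each follow a different part of Appendix 2 and both claim to be compliant. A reader of the final report could not tell whether a low count of mild bleeding meant few events or few recorded events.

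**Working it through.** The plan states no figure that needs reproducing here. The check sets the passages side by side.

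**1. Which column of the rule applies.** Section 22 describes an open-label phase II study, so the Phase II entries of the table govern this trial.

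**2. The cells.** The Unrelated row begins "Unrelated Phase I Phase I Phase I Phase II": Phase I at Grade 1, Phase I at Grade 2, and Phase II first appearing at Grade 3. The Unlikely row begins the same way: "Unlikely Phase I Phase I Phase I Phase II". The Possible row, by contrast, carries Phase II from Grade 1: "Possible Phase I Phase II Phase III". Parts of the table are broken by text extraction, but the Grade 1 to 3 cells of the two rows in question are legible.

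| Attribution | Grade | Appendix 2 definition | Appendix 2 table, Phase II |
|---|---|---|---|
| Unrelated | 1 | report | not listed |
| Unrelated | 2 | report | not listed |
| Unlikely | 1 | report | not listed |
| Unlikely | 2 | report | not listed |
| Unrelated, Unlikely | 3-5 | report | listed |
| Possible, Probable, Definitive | 1-5 | report | listed |

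The conflict is confined to 2 attributions × 2 grades = 4 cells. No text says which rule prevails.

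**3. The attribution scale.** Unlikely decides whether a Grade 1-2 event is recorded under the table, but the causality text defines only Unrelated and Related. The documents do not say how five levels map to two.

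**4. Does the bleeding risk fall in these cells?** By the appendix's own equivalence, mild to moderate is Grade 1-2, so the grade condition is met. The attribution condition is met only when the investigator judges the bleeding unrelated or unlikely. The AESI route does not cover bleeding, and it covers anemia only when treatment-related.

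**5. Which summaries are exposed.** Section 3.7 reports 364 of 377 patients (364/377 = 96.6%) with a treatment-emergent event of any grade and cause. A rate built under the table would not be the same quantity. The other main rates there are defined by relatedness: treatment-related Grade 3 or higher 15.4%, treatment-related serious events 7.4%, discontinuations for treatment-related events 4.2%, treatment-related immune events 9.0%, treatment-related anemia events 6.4%. The table records possibly related or stronger at every grade, so these remain comparable, assuming Unlikely is counted as not related.

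**6. The stopping rule.** The unacceptable toxicities in Section 23 are deaths, severe or major perioperative events, and treatment-related delays to surgery. None is a Grade 1-2 event judged unrelated or unlikely.

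**7. Size.** The documents give no bleeding rate and no split of low-grade events by attribution, so no expected loss can be calculated. The resolution of the trial is 1/23 = 4.3 percentage points per patient.

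**The case against.** The case on the other side has force.

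- The table is headed as a recommendation and covers Phases I to III, so it looks generic, whereas the definition is worded as a requirement. A site that follows the definition omits nothing. This stands: the table permits the omission and does not order it.
- Other text points towards full capture. Section 11.3 has symptoms and adverse events of all patients graded at scheduled intervals. The Section 21 calendar calls for CTCAE documentation throughout the study, and again after surgery, with no filter on grade or cause. Appendix 2 requires serious events to be reported to the IND Office regardless of attribution. A reader might infer that low-grade unrelated bleeding has no route into the record; these sections show otherwise. They do not say that the table is overridden, so the conflict remains.
- A reader might also infer that hemoptysis in lung cancer will usually be put down to the tumour and dropped. The documents do not support that. Appendix 2 does list the course of the underlying disease as a causality factor, but it also lists known side effects of the drug. It reserves Unrelated for events that could not medically be attributed to the drug, as well as requiring an alternative explanation. For a named drug risk, this leans towards Related.
- No decision rule depends on these events. The primary endpoint is major pathologic response, and Section 22 makes the secondary analyses descriptive. This stands and limits the weight of the point.

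**Conclusion.** The contradiction is real, lies within one appendix of the current text, and should be corrected. If the table is followed, Grade 1-2 events judged unrelated or unlikely may be missing from the toxicity data. All-cause rates, mild-to-moderate mucosal bleeding among them, may then be understated and could not be compared with the 96.6% any-event figure. The conclusion is conditional on the table being applied, which the documents leave open.

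The effect is limited to four cells. Treatment-related rates, serious events, AESIs and the toxicity stopping rule are not affected. It is tempting to set 96.6% against 15.4% in Section 3.7 and conclude that most events sit in the affected grades. That does not follow: the first counts patients with any event of any cause and grade, the second counts patients with treatment-related Grade 3 or higher events, and the gap mixes grade with attribution. The size of any understatement therefore cannot be stated from these documents.

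**What to change.** Reconcile the three parts of Appendix 2.

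1. State that the definition governs: adverse events of all grades and attributions are recorded from the first protocol intervention, the start point the definition already uses, to the End-of-Treatment visit. Keep the Section 11.3 exclusion of usual surgical events such as expected pain and bleeding, and the appendix's existing limits on laboratory findings and disease progression.
2. Add Phase II to the four cells (Unrelated and Unlikely, Grades 1 and 2), or remove the table.
3. Use one attribution scale throughout. If five levels are kept, define each and say which count as related in the treatment-related summaries.

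The cost is a wording change in Appendix 2 and modest extra data entry for 23 patients at one site. It should be made prospectively, because mild events that were not recorded at the time may not be fully recoverable later.
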